## Hippocampal Volume

Baseline and demographic characteristics were summarized by standard descriptive statistics. Neurocognition scores were converted to fully-demographically corrected T-scores. These scores have a mean of 50 and an SD of 10 and compare the score of the test-taker to those in the NIH Toolbox nationally representative normative sample, while adjusting for key demographic variables collected during the NIH Toolbox national norming study. Fully corrected T-scores represent an individual's level of cognitive functioning compared to age-, education-, sex-, and race/ethnicity-matched peers. Higher fully corrected T-scores indicate better performance. We tested change from baseline to follow-up in hippocampal volume and neurocognition using linear mixed models with maximum likelihood. We also explored whether, within the BWL group, baseline or change in hippocampal volume and neurocognition were correlated with percent weight loss. Statistical significance was defined as  $p < 0.05$  for all outcomes.

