10.2 MEDICAL MONITORING.....	4
10.2.1 Data and Safety Monitoring Plan	4
10.2.2 DATA SAFETY MONITORING BOARD	4
11 STUDY ADMINISTRATION, DATA HANDLING AND RECORD KEEPING	4
11.1 CONFIDENTIALITY	4
12 PRIVACY	4
13 STUDY MONITORING, AUDITING, AND INSPECTING	4
14 ETHICAL CONSIDERATIONS	5
14.1 RISKS	5
14.2 BENEFITS	7
14.3 RISK BENEFIT ASSESSMENT	7
14.4 INFORMED CONSENT PROCESS / HIPAA AUTHORIZATION	8
15 STUDY FINANCES	8
15.1 CONFLICT OF INTEREST	8
15.2 SUBJECT STIPENDS OR PAYMENTS	8
16 REFERENCES	8

CONFIDENTIAL

This material is the property of the University of Pennsylvania.

Study Summary

Title	A Randomized Controlled Trial Examining the Neurocognitive Benefits of a Nationally Available Weight Management Program
Short Title	Neurocognitive Benefits of WW
IRB Number	834404
Phase	Phase 4
Methodology	Randomized, wait-list controlled, open label
Study Duration	1.5 years
Study Center(s)	Single-center
Objectives	To assess the effects of a commercially available weight loss program (WW, formerly Weight Watchers) on neural response to food cues and memory tasks, as well as on structural brain morphology.
Number of Subjects	60
Main Inclusion and Exclusion Criteria	Key Inclusion: BMI \geq 30 kg/m ² ; female; ages 18-60 Key Exclusion: Weight > 158.8 kg; pregnancy or lactation; current psychiatric disorder that significantly interferes with daily living; active suicidal ideation; presence of conditions that may interfere with magnetic resonance imaging; use of weight loss medications or other agents known to affect body weight or blood glucose in the past 3 months; type 1 or 2 diabetes mellitus; visual, auditory, or other impairment affecting task performance
Reference therapy	Wait-list control group
Statistical Methodology	Mixed-effects linear models
Safety Evaluations	Adverse events
Data and Safety Monitoring Plan	Drs. [name] and the co-investigators will be responsible for monitoring the data quality and the ongoing safety of subjects. A data safety monitoring board will also monitor the data quality and ongoing safety of subjects.

BACKGROUND AND STUDY RATIONALE

Introduction

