Thus, current evidence suggests that weight loss programs that encourage moderate caloric restriction and increased physical activity may improve neural responses to food cues. Furthermore, decreased neural reward responsiveness to high-calorie food cues and increased responsiveness to low-calorie food cues may underlie improvements seen in self-reported and behavioral measures of appetite. Behavioral weight loss studies also suggest that weight loss induced through diet, physical activity, and lifestyle changes can improve brain structures and function associated with memory. However, this literature is limited by small sample sizes and the lack of randomized trials that have directly assessed these questions. The present study is significant because it will help to improve our understanding of neuronal correlates of weight loss interventions. A better understanding of brain mechanisms underlying weight loss can improve the efficacy of obesity prevention and treatment interventions.

2 Study Objectives

The purpose of the present study is to conduct a randomized controlled trial (RCT) to assess the effects of a commercially available weight loss program (WW; formerly Weight Watchers) on neural response to food cues and memory tasks, as well as on structural brain morphology. Participants with obesity will be randomized to either 16 weeks of a group-based WW program (n=30) or a wait-list control (WLC; n=30). Both groups will have structural and blood oxygen level-dependent (BOLD) functional magnetic resonance imaging (fMRI) scans at baseline and after the end of the intervention. Participants will complete the following fMRI tasks: 1) structural scans; 2) food cue task to measure reactivity to high and low-calorie food images;¹⁰ and 3) N-back task to measure working memory (i.e., the ability to temporarily hold information available for processing).⁵⁴ In addition, participants will complete self-report and behavioral measures of eating behaviors, appetite, physical activity, mood, quality of life, attention and memory at baseline, and weeks 8 and 16 (and at the end of the intervention).

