2.1 Primary Objectives

Aim 1: To compare differences between the WW and WLC groups at the end of the intervention in changes in BOLD fMRI response to food cues.

Hypothesis 1: We hypothesize that compared to the WLC, the WW group will have significantly greater declines in BOLD response to high-calorie foods in the reward regions of the brain (insula, orbitofrontal cortex, anterior cingulate cortex, nucleus accumbens) and significantly greater increases in BOLD response to low-calorie foods in these reward regions.

Aim 2a: To compare differences between the WW and WLC groups at the end of the intervention in changes in self-reported and behavioral measures of appetite, and **Aim 2b:** to test whether changes in self-reported and behavioral measures of appetite are associated with changes in neural responsivity to high and low-calorie foods in each study arm.

Hypothesis 2a: We hypothesize that at the end of the intervention the WW group, compared to the WLC group, will have significantly greater declines in self-reported reward-based eating, food cravings, hunger, and preference for high-calorie foods, and significantly greater increases in fullness after meals and preference for low-calorie food. *Hypothesis 2b:* We hypothesize that in the WW group, greater declines in BOLD responses to high-calorie foods will be associated with decreased (self-reported) wanting, liking, preference and craving of these foods, and that greater increases in BOLD response to low-calorie foods will be associated with increased wanting, liking, preference, and craving of low-calorie foods.

CONFIDENTIAL

This material is the property of the University of Pennsylvania.

Aim 3: To evaluate whether WW, compared to WLC, increases hippocampal volume from baseline to the end of the intervention.

Hypothesis 3: We hypothesize that compared to the WLC, WW will be associated with a significantly greater increase in the size of the hippocampus.

Aim 4: To compare differences between the WW and WLC groups at the end of the intervention in changes in BOLD fMRI response to the N-back task.⁵⁴

Hypothesis 4: We hypothesize that during the working memory task, the WW group, relative to the WLC group, will have significantly greater increases in BOLD activation in the hippocampus, dorsolateral and midventrolateral prefrontal cortex, posterior parietal cortex, and premotor cortex.

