3.1.1 Primary Study Endpoints

The primary endpoints are baseline to end of intervention changes in BOLD fMRI response to food images and to the N-back task as well as baseline to end of intervention changes in hippocampal volume and appetite (i.e., reward-based eating, food cravings, hunger, preference for high- and low-calorie food, and fullness).

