5.1 Total Number of Subjects and Sites

This is a single-site study. We will randomly assign 60 females with obesity to either WW or a WLC.

5.2 *Inclusion Criteria*

- Ages 18-60 years
- Female
- $BMI > 30 \text{ kg/m}^2$
- Eligible female patients will be:
 - non-pregnant
 - non-lactating
 - surgically sterile or postmenopausal, or they will agree to continue to use an accepted method of birth control during the study
Acceptable methods of birth control are: hormonal contraceptives; double barrier method (condom with spermicide or diaphragm with spermicide); intrauterine device; surgical sterility; abstinence; and/or postmenopausal status (defined as at least 2 years without menses).
- Participants must:
 - understand and be willing to comply with all study-related procedures and agree to participate in the study by giving written informed consent

5.3 *Exclusion Criteria*

- Weight $> 158.8 \text{ kg}$ (350 lbs, due to scanner weight restrictions)
- Serious medical risk such as type 1 or 2 diabetes, cancer, or recent cardiac event (e.g., heart attack, angioplasty)
- Untreated thyroid disease or any changes (type or dose) in thyroid medication in the last 6 months
- Current psychiatric disorder that significantly interferes with daily living
- Active suicidal ideation
- Current substance use disorder (current or in remission < 1 year)
- Presence or history of orthopedic circumstances, metallic inserts, pacemaker, claustrophobia, or other conditions that may interfere with magnetic resonance imaging
- Participation in a structured weight loss program in the prior 6 months
- Active WW member within the past 12 months

CONFIDENTIAL

- Use of medications known to induce significant weight loss/gain, including chronic use of oral steroids in the past 3 months
- Psychiatric hospitalization within the past 6 months
- Loss of ≥ 10 lbs of body weight within the past 3 months
- History or plans for bariatric surgery
- Visual, auditory, or other impairment affecting task performance
- Epilepsy
- Neurological trauma (e.g., concussion)
- Inability to attend treatment and/or assessment visits
- Participant from same household
- Adherence to specialized diet regimes, such as vegetarian, macrobiotic
- Lack of capacity to provide informed consent
- Inability to walk 5 blocks comfortably or engage in some other form of aerobic activity (e.g., swimming)

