6.6 Randomization Visit

Participants who meet all eligibility criteria assessed at the screening visit will be scheduled for a baseline fMRI assessment. The visit will occur within approximately 4 weeks of beginning treatment. They will be instructed to complete the self-reported outcomes either online (using a link e-mailed to them) or using paper-and-pencil questionnaires (for those who prefer this method) approximately 10 days before their fMRI scan. Their questionnaires will be reviewed for completeness at the fMRI visit, with any omissions or errors corrected. The randomization visit will include a weight, waist circumference, blood pressure, and heart rate, and completion of additional baseline assessments (as described in Table 2). Participants will then be randomly assigned to the two groups in equal numbers (i.e., 1:1 ratio). This will be accomplished using a computer-generated algorithm operated by faculty at the Center for Weight and Eating Disorders at the University of Pennsylvania (e.g., [name]). Assignment will be made from randomly varied block sizes (2 or 4). This is an open-labelled randomized trial. Due to COVID-19, we have combined the randomization visit with the baseline fMRI visit. After they complete their fMRI visit, they will be randomized to a treatment group.

CONFIDENTIAL

This material is the property of the University of Pennsylvania.

Table 1. Schedule of Study Assessments and Treatment Visits

	Weeks																																	
	8	9	10	11	12	13	14	15	16	17	18	19	20	21	22	23	24	25	26	27	28	29	30	31	32	33	34							
Screening																																		
FMRI Assessment																																		
Cognitive, Behavioral, and Self-report Assessments																																		
Randomization Visit																																		
WW Group Treatment																																		
WLC Group Treatment																																		

*WLC group only. For participants affected by COVID-19 and subsequent mandates necessary to help mitigate the transmission of the virus (e.g., stay-at-home orders), their fMRI assessments will occur at the end of the intervention. They will have questionnaire assessments administered at week 16 and then again at the end of the intervention when they can have their fMRI scan. The randomization visit will now be combined with the fMRI visit.

Table 2. Schedule of Procedures

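### Minor: the SAP names maximum likelihood for the hippocampal volume model, which, read literally and for a two-sided group-by-time contrast in 60 complete pairs, makes the SE 1.7% too small and type I error 5.4% to 5.9%

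*SAP*

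**What the plan says.** The SAP, under Hippocampal Volume, states: "We tested change from baseline to follow-up in hippocampal volume and neurocognition using linear mixed models with maximum likelihood". It sets significance at p < 0.05 "for all outcomes". That section does not list the fixed effects. It also does not state the test statistic, the degrees-of-freedom method, whether the test is two-sided, or the number of women with both scans.

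No other part of the supplied documents names an estimator. The protocol's Study Summary gives only "Mixed-effects linear models". The SAP's Food Cues section lists time, group and their interaction for the regions of interest but does not say how those models were estimated.

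The endpoint is a primary one. Aim 3 in protocol section 2.1 is "To evaluate whether WW, compared to WLC, increases hippocampal volume from baseline to the end of the intervention", and section 3.1.1 counts "baseline to end of intervention changes in hippocampal volume and appetite" among the primary endpoints. On size, section 5.1 says: "We will randomly assign 60 females with obesity to either WW or a WLC". Section 2 gives 30 per arm, with a structural scan at baseline and another after the intervention.

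**The concern.** ML estimates a variance as if the fixed effects were known. In a large trial this makes no visible difference. With at most 60 women and one change per woman, the residual variance is divided by a number that is slightly too large, so the standard error and the confidence interval are slightly too small. REML removes this bias. Nothing in the SAP's description offsets it, since no small-sample degrees-of-freedom method is named.

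At stake is a small tilt towards significance on a primary endpoint tested at an unadjusted 0.05.

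**Working it through.** The documents give no power or error-rate figure for this analysis, so there is none to reproduce.

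**Inputs from the documents.** n = 60 women, 30 per arm (protocol sections 2 and 5.1); two structural scans each (section 2); comparison of WW with wait-list on change (Aim 3); alpha 0.05 (SAP, Hippocampal Volume).

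**Assumptions, because the SAP is silent.** Fixed effects are group, time and group by time, with no covariate-by-time term. The test is two-sided. Every woman has both scans.

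**Step 1: standard error.** With two visits and complete pairs, the group-by-time test is the two-sample comparison of change scores. ML divides the residual sum of squares by n, REML by n − 2. The SE ratio, ML to REML, is sqrt((n − 2)/n) = sqrt(58/60) = 0.9832, so the ML standard error is 1.7% too small. Random-intercept models fitted both ways to 20 simulated data sets gave 0.9832 each time.

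**Step 2: type I error.** REML with t on 58 df is exact here. Under ML the test rejects when |t58| exceeds c × 0.9832, where c is the critical value used.

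| Test, n = 60 | Rejects when \|t58\| exceeds | Type I error |
|---|---|---|
| REML, t58 | 2.0017 | 5.00% |
| ML, t58 | 2.0017 × 0.98319 = 1.9681 | 5.38% |
| ML, likelihood ratio: 60 × log(1 + t²/58) > 3.8415 | 1.9583 | 5.50% |
| REML, normal | 1.960 | 5.48% |
| ML, normal | 1.960 × 0.98319 = 1.9270 | 5.89% |

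With a normal reference, 5.48 − 5.00 = 0.48 points come from the reference and 5.89 − 5.48 = 0.41 from ML.

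Two simulations of 400,000 null data sets each gave 5.36% and 5.29% for ML with t58, and 5.86% and 5.80% for ML with a normal reference. The simulation standard error is about sqrt(0.0538 × 0.9462/400,000) = 0.04 points. The closed-form values are exact and are the ones relied on.

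**Step 3: when a conclusion changes.** The same thresholds answer this. The ML result is significant and the correct one is not only if the correct p-value lies between .050 and .054 (t58), .055 (likelihood ratio) or .059 (normal).

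**Step 4: fewer pairs.** The number of completers is not given, so 45 is an assumption. sqrt(43/45) = 0.9775, a shortfall of 2.2%. Type I error is 5.51% (t43), 5.68% (likelihood ratio) and 6.20% (normal).

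**Step 5: other model forms at n = 60, complete pairs.** The shortfall is unchanged at 1.7% with two baseline covariates that do not interact with time. It is 1.4% to 1.6% with a common baseline mean (between-visit correlation .95 to .5 giving 1.6% down to 1.4%). With one covariate-by-time term it is 2.5%, since sqrt(57/60) = 0.9747, and type I error is 5.59% with t57. For within-arm change in 30 women it is 1.7%, since sqrt(29/30) = 0.9832. Every form checked errs in the same direction; nothing is claimed for others.

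**The case against.** The strongest objection is that this hardly matters. ML is a legitimate and widely used estimator, and naming it is not in itself a mistake. The cost is about 0.4 points of type I error and 1.7% of interval width. In the same SAP section, the unwritten between-arm term and the single 0.05 threshold for all outcomes are more consequential gaps. This stands, and it is why the point is rated minor.

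Second, the figures belong to an assumed analysis, because the SAP gives neither the fixed effects nor the reference distribution. This also stands: 1.7% and 5.4% to 5.9% are conditional. The alternatives checked move the shortfall only between 1.4% and 2.5% at n = 60 and do not reverse its direction.

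Third, the phrase may be loose shorthand that covers REML. That is possible. No other text settles it, so the wording needs clarifying either way.

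A reader might go further and infer that type I error is 5.9%. The documents do not support this. They name no reference distribution, and more than half of the excess at 5.9% comes from the normal reference rather than from ML.

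**Conclusion.** The point holds as a minor one. Taken literally, the SAP's estimator gives slightly anti-conservative inference on a primary endpoint: SE 1.7% too small, and type I error 5.4% (t58), 5.5% (likelihood ratio) or 5.9% (normal), against 5.0% for REML with t58. This rests on a two-sided group-by-time contrast, no covariate-by-time term and 60 complete pairs.

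A reader might infer that the hippocampal result is unreliable, or that all the trial's mixed models share the fault. Neither follows. Only a correct p-value just above .050 would be affected. The Food Cues section names no estimator, and no size has been worked out for the neurocognition models, although the same sentence covers them.

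**What to change.** Fit the hippocampal group-by-time contrast by REML with Kenward-Roger or Satterthwaite degrees of freedom, and report it with its 95% CI. State the estimator and the degrees-of-freedom method in the SAP. If REML was in fact used, correct the text. If the ML result is kept, show the REML result beside it and say whether the conclusion changes.

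The cost is one refit with a different estimation option and one sentence. At n = 60 the interval widens by 1.7% if t58 was already used (sqrt(60/58) = 1.0171), or by 3.9% if a normal reference was used (2.0017/1.9270 = 1.0388), with a matching slight loss of power. Point estimates are identical for the group, time and group-by-time model with complete pairs. Under a common baseline mean they differ by only about 0.01 SE. With 60 baseline and 45 follow-up scans (an assumption) they differed by at most 0.004 SE in 180 simulated fits.

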4.1 General Design

The proposed investigation is an open-label, RCT to assess changes in neural responses to food images and memory tasks in 60 participants with obesity who are randomized to a 16-week behavioral weight loss program (WW; n=30) versus a WLC group (n=30). Participants will be assessed at baseline and 16 weeks and at the end of the intervention, with the baseline and end of intervention assessments including structural and functional neuroimaging with BOLD fMRI. An additional assessment will occur at week 8 and include self-report measures only. Neither subjects nor investigators will be masked to treatment assignment.

CONFIDENTIAL

COVID-19 Changes. Due to the mandatory restrictions in research related to COVID-19, we have transitioned our in-person groups to group-based, remotely delivered sessions via Blue Jeans. We are also not able to conduct fMRI scans on participants and have extended weekly treatment for those people who are currently in the intervention arm (currently our first cohort of 10 participants). Extending treatment will help participants in the intervention arm continue to lose weight, which is an important mechanism we believe will be related to the fMRI results. The treatment will continue as it has, with remotely-delivered, group-based, behavioral weight loss sessions. Those on the wait-list have also had an extended time on the wait-list until we are able to conduct in-person, group treatment in accordance with University Guidance. We will administer the questionnaires at week 16 as in the original protocol. However, we will re-administer these questionnaires at the end of the intervention, once we are able to conduct fMRI scans on participants.

5 Study Population and Duration of Participation

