5.4 Duration of Study Participation

The maximum amount of time subjects in the WW group will participate in the study is 45 weeks (screening which may be up to 4 weeks before baseline fMRI; baseline fMRI which may occur up to 4 weeks before start of intervention; 16 to 36-week intervention; final fMRI up to 1-week post intervention period). The maximum amount of time the WLC subjects will participate in the study is 61 weeks (screening which may be up to 4 weeks before baseline fMRI; baseline fMRI which may occur up to 4 weeks before start of wait-list; 16 to 36 weeks on wait-list; final fMRI up to 1 week post wait-list period; 16 week intervention).

5.5 Vulnerable Populations:

Children, pregnant women, fetuses, neonates, or prisoners are not included in this research study.

6 Study Procedures

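### The exploratory correlation of hippocampal and cognitive change with percent weight loss in the BWL arm takes no account of programmes and scan intervals that run from 16 to 36 weeks

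*SAP*

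**What the plan says.** The SAP (Hippocampal Volume) first gives the main model: "We tested change from baseline to follow-up in hippocampal volume and neurocognition using linear mixed models with maximum likelihood". It then adds the analysis at issue: "We also explored whether, within the BWL group, baseline or change in hippocampal volume and neurocognition were correlated with percent weight loss". No covariate, stratum or scan interval is named for it, nor the visit at which percent weight loss is taken. The section sets the significance level at 0.05 "for all outcomes". BWL in the SAP is the WW arm of the protocol.

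The protocol shows that this arm did not receive a programme of one length:

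- Section 5.4 describes a "16 to 36-week intervention; final fMRI up to 1-week post intervention period".
- Section 4.1 (COVID-19 Changes) says that weekly treatment was extended for the women then in the intervention arm, a first cohort of 10, because scans could not be done. It gives the expected result: "Extending treatment will help participants in the intervention arm continue to lose weight". The wait-list period was lengthened as well.
- The notes to Tables 1 and 2 place the scan of affected participants at the end of the intervention, with questionnaires at week 16 and again at that later visit.
- Section 6.4 reduces the week 8 visit to self-report under the COVID restrictions, so the cognitive battery was not given there.

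**The concern.** Programme length varies within the arm up to 36/16 = 2.25-fold, and the interval between scans varies with it. The protocol itself links length to weight loss, which is one variable in the correlation. The other variable, change in hippocampal volume or cognition, could also vary with length or cohort for reasons unrelated to weight: a longer time between scans, a longer retest interval, or one fewer earlier exposure to the cognitive battery. If both links exist, pooling the women produces a correlation that partly reflects cohort.

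At stake is interpretation. A within-arm correlation with weight lost is readily taken as dose-response evidence that losing more weight brings more brain or cognitive benefit. Cohort differences could create that pattern. If the non-weight effect ran the other way, they could mask a real one. Randomisation offers no protection here, because the comparison is among women in the same arm.

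**Working it through.** The documents give no power, sample size or expected value for this correlation, so there is no planned figure to reproduce. The durations in section 5.4 do add up: 4 + 4 + 36 + 1 = 45 weeks for WW, and 4 + 4 + 36 + 1 + 16 = 61 weeks for the wait-list.

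**Inputs**

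- From the documents: 30 women randomised to WW (protocol sections 2 and 4.1); 10 extended when section 4.1 was written; level 0.05 (SAP), taken as two-sided.
- Assumed: all 30 analysed and 10 finally extended, so p = 1/3; two groups of programme length; normal data with unit SD within cohort.
- Assumed: the extended cohort differs by d1 SD in weight loss and by d2 SD in brain or cognitive change through a route other than weight loss. Neither is in the documents. The range examined is 0.5-1.5 for d1 and 0-1.0 for d2.

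**Induced correlation with no association within cohort**

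r = q·d1·d2 / √[(1 + q·d1²)(1 + q·d2²)], with q = p(1 − p) = (1/3)(2/3) = 0.222.

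For d1 = d2 = 1: r = 0.222 / 1.222 = 0.18. For d1 = 1.5, d2 = 1: r = 0.333 / √(1.5 × 1.222) = 0.25. Reversing the sign of d2 reverses the sign of r, so the bias can go either way. At n = 30, |r| must exceed 0.361 to reach p < 0.05.

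**False-positive rate at nominal 5%** (simulation, n = 30, 10 extended; 20,000 or 40,000 draws)

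| d1 (weight loss) | d2 (other route) | Induced r | Unadjusted |
|---|---|---|---|
| 1.0 | 0 | 0.00 | 5.0% |
| 0.5 | 0.25 | 0.03 | 5.1% |
| 0.5 | 0.5 | 0.05 | 5.7% |
| 1.0 | 0.5 | 0.10 | 8.0% |
| 1.0 | 1.0 | 0.18 | 16.4% |
| 1.5 | 1.0 | 0.25 | 26.5% |

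Adjusting for cohort gives about 5% in every row. If 15 of 30 were extended, the rate at 1.0/1.0 would be 19.0%.

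**What adjustment costs if there is no confounding**

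Take a true within-cohort correlation of 0.4 and d2 = 0, so that cohort acts only through weight loss. Cohort then carries q·d1²/(1 + q·d1²) of the variance in weight loss: 0.222/1.222 = 18% at d1 = 1, and 0.5/1.5 = 33% at d1 = 1.5. Adjustment discards that share. Simulated power falls from 69% to 59% (10 points) at d1 = 1, and from 78% to 59% (19 points) at d1 = 1.5.

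**The case against.** The strongest reply is that only half of the confounding path is documented. The protocol expects extension to increase weight loss. Nowhere does it say that extension changes the hippocampus or cognition by another route, and section 4.1 presents weight loss as the mechanism. If longer treatment leads to more weight loss and that leads to brain change, the cohort contrast is signal, and the d2 = 0 row shows no false positives beyond 5%. This stands, and it makes the concern conditional.

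Three further objections also stand in part:

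- The larger rates need a full 1 SD difference unrelated to weight, for which the documents give no figure.
- The return to 5% after adjustment is partly built in, because the simulation adjusts for the same two-group variable that generated the bias.
- The analysis is labelled exploratory and is not among the protocol's aims or endpoints. Any correlation with achieved weight loss is observational and open to other confounders, such as adherence.

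None of this removes the gap. Length is linked to weight loss by the protocol's own expectation, scan timing follows length by design, and the plan offers no way to tell the two readings apart.

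A reader might infer that cohort is an established common cause, so that the plain correlation is invalid and should be replaced. The documents do not support that: the second link is plausible but not shown, and replacement would give up power and possibly real signal. Nor does a clean 10/20 split have support as fact, since the 10 is a count at the time of writing and the final number extended is not given.

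**Conclusion.** The point holds as a conditional weakness of an exploratory analysis. The change correlations pool programmes and scan intervals of 16 to 36 weeks without accounting for the difference, and they can be biased in either direction if length or cohort acts on brain or cognitive change other than through weight loss.

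With 10 of 30 extended, the inflation is small (about 5-8%) for non-weight differences up to 0.5 SD with weight loss differing by up to 1 SD. It becomes material (16-27%) only at 1 SD with weight loss differing by 1-1.5 SD. It is nil if cohort acts only through weight loss. All of these sizes rest on assumed cohort differences.

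Two wider inferences should be resisted. Programme length cannot alter baseline values, so the baseline correlations named in the same SAP sentence are not affected by it. The between-arm comparison is largely protected, because the wait-list was extended too.

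**What to change.** Keep the unadjusted correlation. Beside it, for the change measures only, pre-specify one partial correlation adjusted for weeks between scans. State that percent weight loss is taken at the same end-of-intervention visit as the scan, because week 16 and the end of the intervention differ for extended women. Report the number of women by programme length and plot the points by cohort. Describe the result as a weight-loss association only if the two estimates agree.

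Name a single adjuster: offering weeks or cohort as alternatives would add analyst choice.

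The cost is a sentence or two in the SAP, one extra analysis using scan dates the trial should already hold, and one degree of freedom. The adjusted estimate is also less powerful (about 10-19 percentage points in the cases above) and may remove real signal where longer treatment works through weight loss. That is why it supplements the unadjusted value.
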